### **Acknowledgements:**

The CTRI is partially supported by the National Institutes of Health, Grant UL1TR001442 of CTSA funding, as well as by Helsinn Therapeutics (U.S.), Inc (funding and study drug)

## LIST OF ABBREVIATIONS

AE	Adverse Event
ALT	Alanine transaminase
ASCO	American Society of Clinical Oncology
AST	Aspartate Transaminase
CINV	Chemotherapy-Induced Nausea & Vomiting
CTCAE	Common Terminology Criteria for Adverse Events
CTRI	Clinical and Translational Research Institute
CYP3A4	Cytochrome P450
DSMB	Data and Safety Monitoring Board
ECOG	Eastern Cooperative Oncology Group
EKG	Electrocardiogram
FDA	Food and Drug Administration
FLIE	Functional Living Index for Emesis
HEC	Highly Emetogenic Chemotherapy
HIPAA	Health Insurance Portability and Accountability Act
HRPP	Human Research Protections Program
ICH	International Conference on Harmonization
IDS	Investigational Drug Services
IQR	Interquartile Range
IRB	Institutional Review Board
MASCC	Multinational Association of Supportive Care in Cancer
MEC	Moderately Emetogenic Chemotherapy
NCCN	National Comprehensive Cancer Network
NCI	National Cancer Institute
NK1	Neurokinin-1
SAE	Serious Adverse Event
SD	Standard Deviation
5-HT 3	5-hydroxytryptamine-3

**STUDY SCHEMA**

**STUDY SUMMARY**

Title	Fixed-Dose Combination of Netupitant and Palonosetron (Akynzeo®) in the Treatment of Refractory Chemotherapy-Induced Nausea and Vomiting
Short Title	Akynzeo® in the Treatment of Refractory CINV
Phase	II
Methodology	Single-arm, single-center, open-label study
Study Duration	The anticipated total study duration is 24 months from fully-executed contract and IRB approval. Individual subject participation is limited to approximately 1 week.
Study Center(s)	UC San Diego (UCSD) Moores Cancer Center UCSD Medical Center - La Jolla
Objectives	
Primary: To determine the feasibility of using a fixed-dose combination of netupitant and palonosetron (Akynzeo®) in the treatment of refractory CINV. For this study, refractory CINV is defined as nausea and/or vomiting that occurs after the first cycle of cancer targeted therapy despite guideline-based prophylaxis and after first-line rescue medication with either a dopamine receptor antagonist, steroid, and/or benzodiazepine.
 
Hypothesis: Feasibility, defined as more than 70% of selected study subjects completing all study related procedures, will be achieved.
 
Secondary:
 
 
• To evaluate the occurrence of adverse events using the National Cancer Institute Common Terminology Criteria for Adverse Events (CTCAE) version 4.03.
 
• To evaluate complete response defined as no emesis and no use of rescue medication for 5 days after Akynzeo® administration.
 
• To characterize 24-hour intervals of CINV using the MASCC Antiemesis Tool (MAT).
 
• To evaluate 5-day health related quality of life recall using the Functional Living Index for Emesis (FLIE) scale.
 
• To evaluate healthcare resource utilization as defined by the number of emergency room visits, hospitalizations, and infusion center visits encounters regarding signs/symptoms associated with CINV over the seven-day study period.
 
• To evaluate the occurrence of refractory CINV using CINV risk assessment at follow up day 7 compared to treatment day 1.
 
 
Exploratory: To determine patient preference for use of Akynzeo® for future planned chemotherapy utilizing a five-point Likert scale

Number of Subjects	50
Diagnosis and Main	Patients who have histologically-confirmed cancer, and confirmed refractory CINV will be eligible

**Inclusion Criteria**

**Inclusion Criteria:**

1. Adults greater than or equal to 18 years old.
2. Must have a histologically-confirmed cancer diagnosis.
3. Must have refractory CINV defined as nausea and/or vomiting that occurs after the first cycle of cancer targeted therapy despite guideline-based prophylaxis and after first-line rescue medication with either a dopamine receptor antagonist, steroid, and/or benzodiazepine.
4. Eastern Cooperative Oncology Group (ECOG) performance status less than or equal to 2.
5. Life expectancy greater than 3 months.
6. Corrected serum calcium level less than or equal to 10.5 mg/dL.
7. Women of child-bearing potential must agree to use adequate contraception (hormonal or barrier method of birth control; abstinence) prior to study entry, for the duration of study participation, and for 14 days following completion of therapy.
  - A) A woman of child-bearing potential is any female (regardless of sexual orientation, having undergone a tubal ligation, or remaining celibate by choice) who meets the following criteria:
    - i) Has not undergone a hysterectomy or bilateral oophorectomy; or
    - ii) Has not been naturally postmenopausal for at least 12 consecutive months (i.e., has not had menses at any time in the preceding 12 consecutive months)
8. Women of child-bearing potential must have a negative pregnancy test prior to initiating study treatment.
9. Ability to understand and willingness to sign a written informed consent.

**Exclusion Criteria:**

1. Patients with QTc interval greater than 450 ms.
2. Patients with a known hypersensitivity reaction to 5-HT3 receptor antagonists or NK1 receptor antagonists.
3. Patients who have taken any medication classified as a strong CYP3A4 inducer within one week of Study Day 1 or 5 half-lives (whichever is longer) or use of a strong or moderate CYP3A4 inhibitor within one week of Study Day 1 or 5 half-lives (whichever is longer) (see Appendix 2).
4. Patients with severe hepatic impairment as defined as AST/ALT greater than three times the upper limit of normal, and/or total bilirubin greater than 3 mg/dL, and/or Child-Pugh score >9.
5. Patients with severe renal impairment defined as creatinine clearance of 15-29 mL/min and/or diagnosed with Stage 4 chronic kidney disease.
6. Patients with end-stage renal disease defined as creatinine clearance of <15mL/min and/or diagnosed with Stage 5 chronic kidney disease.

	
7. Pregnant or lactating females are excluded from enrollment on this trial.
 
8. Patients unable to swallow oral medications.
 
9. Any other condition that, in the opinion of the investigator, may impact the absorption of oral medications.

Study Product(s), Dose, Route, Regimen
	
Subjects will be allowed to participate only once in the study. Study Day 1 will be the day of Akynzeo® dosing. Subjects will receive a single capsule of Akynzeo® (300 mg of netupitant and 0.5 mg of palonosetron) on Study 1

Duration of administration
	
Study drug (Akynzeo®) is an oral fixed-dose combination of 300 mg of netupitant and 0.5 mg of palonosetron. Akynzeo® will be administered once as an oral capsule and will be supplied as 300 mg netupitant/0.5 mg palonosetron hard gelatin capsules with a white body and caramel cap with “HE1” printed on the body.


Statistical Methodology
	
Ideally, a phase III placebo controlled trial would be completed to demonstrate the efficacy of Akynzeo® in the refractory CINV. However, data regarding pharmacologic interventions for refractory CINV are lacking. Furthermore, it is not established if intervening in the refractory CINV setting is practically feasible. Consequently, we believe a feasibility study is the necessary first step followed by a larger randomized trial.
 
Primary outcome measures and sample size
 
The proposed study is a prospective, single-center, feasibility trial. The primary aim of this study is feasibility – specifically feasibility will be defined as completion of all study procedures over seven days. For the primary aim, we assume an acceptable completion rate from strata of MEC/HEC or tumor types of all study-related procedures would be at least 70%. Assuming a true completion rate of 85%, a sample size of 50 patients would have an 80% power to detect an absolute difference of 15% at Type I error 0.05.
 
Secondary aims
 
Secondary outcome measures including (1) the evaluation of adverse events utilizing the NCI CTCATE v4.03, (2) complete response (no emesis and no rescue medication use), (3) characterization of 24-hour CINV using the MAT, (4) five-day health related quality of life utilizing the FLIE, and (5) healthcare resource utilization (emergency room visits, hospitalizations, and infusion center visits over seven days).
 
(1) Adverse events will recorded in detail and the number of events will be described using n and percent. The severity will be described using means (SD) and medians (IQR) of the adverse event grade (which ranges 0-5).
 
(2) The proportion of patients experiencing complete response will be described with descriptive statistics (n and percent) as well as by using a one-sample confidence interval for proportions, applying the normal approximation to the binomial distribution. In addition, a one-sample z test for proportions will be used to determine if the complete

	
response rate in this sample is significantly different than the 90% seen in previous studies.
 

(3) CINV will be analyzed using the MAT. The MAT consists of 8 distinct items, 4 of these items are binary and will be described using n and percents the other 4 items are continuous (ranging from 0-10) and will be described using mean and SD. Binary variables will also be described using one-sample confidence intervals for proportions (as described in #2 above) and continuous variables will be described using one-sample confidence intervals for means.

(4) Quality of life will be analyzed as a binary response, impact on quality of life vs no impact, a score of less than 54 on the FLIE domain scores and a score of less than 108 on the total score indicates an impact on quality of life. Each domain score, and the total score, will be analyzed separately using a 95% confidence interval to describe the proportion of participants with impacted QoL.

(5) Healthcare resource utilization will be assessed by recording the number of emergency room visits, hospitalizations (with length of stay), and infusion center visits. Each healthcare utilization will be categorized with respect to whether it was specifically related to nausea and vomiting during the seven-day follow up period. A table summarizing the number of each type of utilization related to nausea and vomiting will be provided.

(6) The occurrence of refractory CINV will be analyzed using CINV risk assessment at follow up day 7 compared to treatment day 1.

 
Patient demographic characteristics (age, sex, and patient reported race/ethnicity) will be described using standard descriptive statistics (n/% or mean/SD).
 
As an exploratory aim, regression analysis will be used to develop a predictive model for CINV, based on age, sex, history of >1 alcoholic beverage per day, history of motion sickness, history of hyperemesis gravidarum, and history of anxiety.

--	--

**SCHEDULE OF EVENTS**

	Screening	Treatment (Study Day 1)	Follow-Up (Study Day 2-3) 	Follow-Up (Study Day 4-7) 
Informed consent	X			
Inclusion/exclusion criteria	X			
Demographics	X			
Medical and surgical history	X			
ECOG Performance Status	X			
Confirmed presence of refractory CINV	X			
Serum pregnancy test 	X			
Physical exam with vitals, weight 	X		per routine frequency	
Complete metabolic profile 	X		per routine frequency	
Complete blood count with differential, platelets 			per routine frequency	
EKG QTc evaluation	X 		X 	
Patient CINV risk factors		X		X
Akynzeo® dispensing and administration		X		
Patient medication diary		X		
Collect hospitalization and emergency room visit data		X	X	X
Concomitant medications	X	X	X	X
Adverse event monitoring		X	X	X
MASCC Antiemesis Tool  (MAT)	X	X	X	X
Functional Living Index for Emesis (FLIE) scale 	X	X		X 
Patient preference Likert-scale				X 

 Women of childbearing potential only

 Subjects will be monitored for a total of 6 days following Akynzeo® dosing

 QTc evaluation on Day 3±3 days with single EKG. If patient experiences worsening cardiac symptoms during the study, additional EKG(s) will be performed as clinically indicated

 Complete on Day 5 only

 Daily unless otherwise indicated. Daily safety assessment and hospitalization/ER visit information on Days 2-7 may occur via in-person visit or telephone call from a study team member. Subjects will also receive a daily reminder (via in-person visit or telephone call) to complete required questionnaires/diaries.

 Complete on Day 7 only

 EKG, laboratory and physical exam results obtained within 4 weeks prior to the informed consent date may be used to fulfill study requirements. EKG results may be obtained after screening processes yield positive refractory CINV.

 To be completed daily for 4 days after CINV prophylaxis or Akynzeo® dosing.

 To be completed on the 5th day after CINV prophylaxis or Akynzeo® dosing

## 1.0 BACKGROUND AND RATIONALE

---

### 1.1 Treatment Guidelines for Chemotherapy-Induced Nausea & Vomiting (CINV)

Current treatment guidelines by the Multinational Association of Supportive Care in Cancer (MASCC), National Comprehensive Cancer Network (NCCN), and the American Society of Clinical Oncology (ASCO), have focused efforts on the prevention and treatment of chemotherapy-induced nausea and vomiting (CINV). A standard approach for highly emetogenic chemotherapy (HEC) is to pretreat with a three-drug regimen, including a neurokinin-1 (NK1) receptor antagonist, a 5-hydroxytryptamine-3 (5-HT3) receptor antagonist, and glucocorticoid. In contrast, moderately emetogenic chemotherapy (MEC) pretreatment usually includes a 5-HT3 receptor antagonist and a glucocorticoid. These treatment modalities have focused on the acute (<24 hours) and delayed (>24 hours) phases of CINV. As an NCCN designated and ASCO QOPI cancer center, we follow guideline based recommendations for CINV prophylaxis.

### 1.3 Fixed Dose Combination of NK1 Receptor Antagonist and 5-HT3 Receptor Antagonist

Akynzeo® is an oral capsule containing a fixed-dose combination of 300 mg of netupitant and 0.5 mg of palonosetron. Netupitant is a highly selective NK1 receptor antagonist and palonosetron is a long acting 5-HT3 receptor antagonist. Palonosetron prevents nausea and vomiting during the acute phase and netupitant prevents nausea and vomiting during both the acute and delayed phase after cancer chemotherapy. Single-dose administration of Akynzeo®

in healthy subjects, results in peak plasma concentrations in about 5 hours. Mean elimination half-life in cancer patients was 80±29 hours for netupitant and 48±19 hours for palonosetron. Three phase III clinical trials in over 2,500 chemotherapy-naïve patients evaluating Akynzeo® have recently been published for prevention of CINV over repeated cycles of both HEC and MEC regimens. Akynzeo® was safe, well tolerated, and showed superiority in preventing CINV from HEC and MEC regimens. However, there is no published literature regarding the use of Akynzeo® for the treatment of refractory CINV.

The overwhelming majority of CINV studies have focused on prevention of nausea and/or emesis. However, 15-30% of patients continue to experience CINV despite receiving guideline-based CINV prophylaxis. Refractory CINV represents a an unmet medical need and controlling refractory CINV has the potential to maximize cancer therapy, improve quality of life, and minimize costs associated with healthcare utilization.

## **2.0 STUDY OBJECTIVES**

---

### **2.1 Primary**

To determine the feasibility of using a fixed dose combination of netupitant and palonosetron (Akynzeo®) in the treatment of refractory CINV. For this study, refractory CINV is defined as nausea and/or vomiting that occurs after the first cycle of cancer targeted therapy despite guideline-based prophylaxis and after first-line rescue medication with either a dopamine receptor antagonist, steroid, and/or benzodiazepine.

Hypothesis: Feasibility, defined as more than 70% of selected study subjects completing all study related procedures, will be achieved.

### **2.2 Secondary:**

- To evaluate the occurrence of adverse events using the National Cancer Institute Common Terminology Criteria for Adverse Events (CTCAE) version 4.03.10
- To evaluate complete response defined as no emesis and no use of rescue medication for 5 days after Akynzeo® administration.
- To characterize 24-hour CINV using a modified MASCC Antiemesis Tool (MAT). (**Appendix 1**)
- To evaluate 5-day health related quality of life recall using the Functional Living Index for Emesis (FLIE) scale.
- To evaluate healthcare resource utilization as defined by the number of emergency room visits, hospitalizations, and infusion center visits encounters regarding signs/symptoms associated with CINV over the seven-day study period.
- To evaluate the occurrence of refractory CINV using CINV risk assessment at follow up day 7 compared to treatment day 1.

### **2.3 Exploratory:**

To determine patient preference for use of Akynzeo® for future planned chemotherapy utilizing a five-point Likert scale.

---

### **3.0 PATIENT ELIGIBILITY**

---

#### **3.1 Inclusion Criteria**

1. Adults greater than or equal to 18 years old.
2. Must have a histologically confirmed cancer diagnosis.
3. Must have refractory CINV defined as nausea and/or vomiting that occurs after the first cycle of cancer targeted therapy despite guideline-based prophylaxis and after first-line rescue medication with either a dopamine receptor antagonist, steroid, and/or benzodiazepine.
4. Eastern Cooperative Oncology Group (ECOG) performance status less than or equal to 2.
5. Life expectancy greater than 3 months.
6. Corrected serum calcium level less than or equal to 10.5 mg/dL.
7. Women of child-bearing potential must agree to use adequate contraception (hormonal or barrier method of birth control; abstinence) prior to study entry, for the duration of study participation, and for 14 days following completion of therapy.  
A woman of child-bearing potential is any female (regardless of sexual orientation, having undergone a tubal ligation, or remaining celibate by choice) who meets the following criteria:
  - a. Has not undergone a hysterectomy or bilateral oophorectomy; or
  - b. Has not been naturally postmenopausal for at least 12 consecutive months (i.e., has not had menses at any time in the preceding 12 consecutive months)
8. Women of child-bearing potential must have a negative pregnancy test prior to initiating study treatment.
9. Ability to understand and willingness to sign a written informed consent.

#### **3.2 Exclusion Criteria**

1. Patients with QTc interval greater than 450 ms.
2. Patients with a known hypersensitivity reaction to 5-HT3 receptor antagonists or NK1 receptor antagonists.
3. Patients who have taken any medication classified as a strong CYP3A4 inducer within one week of Study Day 1 or 5 half-lives (whichever is longer) or use of a strong or moderate CYP3A4 inhibitor within one week of Study Day 1 or 5 half-lives (whichever is longer) (see Appendix 2).
4. Patients with severe hepatic impairment as defined as AST/ALT greater than three times the upper limit of normal and/or, total bilirubin greater than 3 mg/dL, and/or Child-Pugh score >9.
5. Patients with severe renal impairment defined as creatinine clearance of 15-29 mL/min and/or diagnosed with Stage 4 chronic kidney disease.
6. Patients with end-stage renal disease defined as creatinine clearance of <15mL/min and/or diagnosed with Stage 5 chronic kidney disease.
7. Pregnant or lactating females are excluded from enrollment on this trial.
8. Patients unable to swallow oral medications.
9. Any other condition that, in the opinion of the investigator, may impact the absorption of oral medications.

## **4.0 TREATMENT PLAN**

---

### **4.1 Subjects and Centers**

A total of 50 subjects, who are 18 years of age or older, have histologically confirmed cancer, confirmed refractory CINV as defined above, an ECOG performance status 0-2, and normal calcium level will be enrolled on this single-center, single-arm study.

### **4.2 Study Design**

This is a Phase II, single-center, single-arm, open-label, feasibility trial using a fixed dose combination of netupitant and palonosetron (Akynzeo®) in the treatment of refractory CINV. The primary aim of this study is feasibility, defined as 70% completion rate of all study procedures over 7 days

## **5.0 Description of Procedures**

---

Eligible subjects will be identified in weekly palliative care patient triage meetings. Patients who are 18 years of age or older, have histologically confirmed cancer, and confirmed refractory CINV will be eligible.

After obtaining written informed consent and verifying that the study subject meets all eligibility criteria, the subject will be enrolled in the study through the UCSD Moores Cancer Center Clinical Trials Office. The study coordinator will educate the subject on how to complete the MASCC Antiemesis Tool (MAT), and FLIE scale after CINV prophylaxis. Subjects will be asked to complete the MAT on a daily basis for 4 days and then the FLIE on the 5th day after cancer treatment. Subjects will be allowed to participate only once in the study. Study Day 1 will be the day of Akynzeo® dosing. Subjects will receive a single capsule of Akynzeo® (300 mg of netupitant and 0.5 mg of palonosetron) on Study 1. Study drug may be taken with or without food. Subjects will complete a study drug diary to document date and time of Akynzeo® administration. On Study Day 1, the study coordinator will educate the subject on how to complete the written MASCC Antiemesis Tool, and FLIE scale, and medication diary for each day following the Study Day 1. An adequate number of copies of each subject questionnaire and diary will be provided to the subject on Study Day 1 for completion at home during the post-treatment observation portion of the study (Study Days 2-7) as needed.

### **5.1 Patient CINV Risk Factors**

Classifying CINV risk by chemotherapy type has provided a valuable framework for the development of international prophylactic antiemetic guidelines. However, considerable work has revealed a number of patient specific variables that may contribute to emetic risk. Therefore, antiemetic guidelines relying solely on emetogenicity of chemotherapy may potentially undertreat patients at higher individual emetic risk than what the chemotherapy alone suggests. CINV patient-related risk prediction models have been developed. Based on data from these models, several key patient risk factors will be collected on Study Day 1 prior to Akynzeo® dosing including: age, sex, alcohol consumption, history and severity of previous CINV, history of morning sickness with pregnancy, history of motion sickness, less sleep the night before chemotherapy, and pre-chemotherapy anxiety.

During the post-treatment observation portion of the study, subjects will receive a daily phone call from a member of the study team to inquire about any adverse event that the subject may

be experiencing and whether they have had any hospitalizations or emergency room visits since the last contact. During these calls, the study team member will also remind the subject to complete the MASCC Antiemesis Tool and medication diary. On Study Day 5 only, the subject will also be instructed to complete the FLIE scale. The subject will be asked to return to clinic on Study Day 3 (+3 days) for a single EKG. Additional clinic visits, physical exams, or laboratory tests performed during the 7-day treatment and follow-up periods will be scheduled according to routine care and according to the subject's treating physician.

Subjects will be asked to return all completed and unused study materials, including subject diaries and questionnaires to a member of the study team at their next routine clinic visit.

A more detailed description of selected assessments is included in the Efficacy Measures and Safety Measures sections.

## 5.2 Removal of Subjects from Study/Study Treatment:

Study subjects may be removed from study treatment or follow-up at any time at their own request or at the discretion of the investigator for any of the following reasons:

- The subject's medical condition worsens or if rescue therapy for subject's CINV fails secondary interventions.
- The investigator believes that study participation is jeopardizing subject's safety.
- The investigator believes that other treatment options may be more beneficial.
- Helsinn or the FDA stops the research due to safety concerns.
- Subject non-compliance with study procedures and requirements.

If a study subject is withdrawn from study participation, the subject will be asked to complete the following study requirements:

- Return unused study materials, including subject diaries and questionnaires.

Discuss future medical care with the investigator

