### **5.5.3 Functional Living Index Emesis (FLIE) Scale**

The FLIE is a validated patient-reported measure of the impact of CINV on daily life, which measures a 5-day recall. The FLIE is a short, self-administered instrument containing two domains, one for nausea (nine items) and one for vomiting (nine items). Responses to each question are rated on a 100mm visual analog scale that is scored on a one to seven-point scale as described in the FLIE scoring manual. A higher score indicates a better quality of life. Minimal or no impact of CINV on daily life will be defined as an average score of more than six on the seven-point scale (i.e. 108 total score or greater than 54 domain score). The FLIE will be completed on the 5th day after CINV prophylaxis, and on the day of Akynzeo® treatment (Study Day 1). During the post-treatment observation portion of the study, the FLIE will be completed on Day 5 only. English and Spanish versions of the MAT will be made available at study activation. Additional foreign translations will be performed as needed.

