### **5.5.4 Healthcare Utilization**

CINV healthcare utilization data including information on the number and location of any emergency room visits, hospitalizations, and infusion center visits will be obtained via phone interview assessment on a daily basis over the seven-day treatment and follow-up periods. Phone calls will reference time since last phone interview and review prior responses. Study subjects will be asked to report all symptoms and problems leading up to the health care contact. All non-UCSD emergency room visits, hospitalizations, or infusion center visits will be followed-up with a medical request to verify the symptoms and reasons for such contacts. Records will be reviewed by study staff, and PI will be consulted for any clarifications. The primary and multiple secondary reasons for emergency room visits, hospitalizations, or infusion center visits will be recorded.

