## **6.0 Study Drug Regimens**

---

Study drug (Akynzeo®) is an oral fixed-dose combination of 300 mg of netupitant and 0.5 mg of palonosetron. Akynzeo® will be administered once as an oral capsule and will be supplied as 300 mg netupitant/0.5 mg palonosetron hard gelatin capsules with a white body and caramel

---

cap with "HE1" printed on the body. All study drug will be supplied by Helsinn, using the current marketed product. IDS will label the study drug with the drug name, study reference number and storage conditions. Study drug will be dispensed to the subject by UCSD Investigational Drug Services (IDS). IDS will be responsible for all study drug shipments and accountability. After refractory CINV is confirmed and all study-related procedures completed on Day 1, subjects will be instructed to take one Akynzeo® capsule. Subjects will be administered a single, oral fixed-dose combination of 300 mg of netupitant and 0.5 mg of palonosetron. Akynzeo® must be kept in a secure place under appropriate storage conditions, as specified on the label and in the Investigator's Brochure. All study drug will be stored in original containers until dispensed to the study patients.

If a patient vomits after taking their Akynzeo® dose within 12 hours and the capsule is expelled from the body intact, it will be considered a missed dose. The patient will be instructed to take a picture of the capsule (if possible) and contact the PI who will determine if the patient should repeat up to one additional dose of Akynzeo®. Any changes from the dosing schedule including missed doses should be recorded in a CRF.

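### Section 5.2 lets follow-up of an already dosed patient be ended for reasons that can track CINV outcome, so the Day 5 FLIE, later MAT days and some visit data may be missing selectively

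*Combined protocol and SAP*

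**What the plan says.** Section 5.2 covers treatment and follow-up in one clause: "Study subjects may be removed from study treatment or follow-up at any time at their own request or at the discretion of the investigator". Two of the listed reasons can relate to how the patient's CINV is going: "The subject's medical condition worsens or if rescue therapy for subject's CINV fails secondary interventions" and "The investigator believes that other treatment options may be more beneficial". The list also includes non-compliance, a safety concern of the investigator, and a stop by the company or regulator. A withdrawn patient is asked for two things: "Return unused study materials, including subject diaries and questionnaires", and a talk with the investigator about future care.

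The assessments affected are set out elsewhere.

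- **FLIE (5.5.3, 6.0).** "During the post-treatment observation portion of the study, the FLIE will be completed on Day 5 only". The Day 1 form comes before the dose: "After refractory CINV is confirmed and all study-related procedures completed on Day 1, subjects will be instructed to take one Akynzeo® capsule".
- **MAT and diary (5.5.1, 5.5.2).** Both are filled in daily by the patient after dosing.
- **Healthcare use (5.5.4).** These data "will be obtained via phone interview assessment on a daily basis over the seven-day treatment and follow-up periods". Outside contacts are then checked: "All non-UCSD emergency room visits, hospitalizations, or infusion center visits will be followed-up with a medical request to verify the symptoms and reasons".
- **EKG (5.1, 7.0).** One is scheduled after dosing, on Day 3 (+3 days) in 5.1 and Day 3±3 days in 7.0.

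Section 9.3 describes the FLIE result as a proportion impacted with a 95% confidence interval. Section 9 gives no analysis set, missing-data rule or sensitivity analysis.

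**The concern.** The drug is given once, with at most one repeat if the capsule is vomited intact within 12 hours (6.0). For almost every dosed patient there is no further treatment to stop, so removal means only that observation ends. Section 5.2 does not separate the two, and no other section available to this review continues the questionnaires, calls or scheduled EKG after removal.

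If the investigator removes patients because their CINV is not controlled, the patients left to complete the Day 5 FLIE and later MAT days are those who did better. The FLIE impact proportion, later nausea scores and the ER and infusion visit counts would then look more favourable than they should. Under 5.3, if feasibility is achieved, the secondary results are searched for trends that could supply an endpoint for a larger Phase II study, so a distortion there could carry forward.

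**Working it through.** **Which data are exposed**

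| Item | After removal on Days 2-4 |
|---|---|
| FLIE | No post-dose value: Day 1 is pre-dose and Day 5 is not reached |
| MAT | Remaining days lost; completed days kept if returned |
| ER and infusion visits | Calls stop. Outside visits without admission are most exposed, because the records request depends on learning of the visit. Visits at the centre may be found in the medical record (9.4) |
| Admissions | Still captured where they qualify as SAEs (8.3), reportable to 30 days after the dose (8.6.1) |
| Adverse events | Monitoring runs to 30 days after the dose (8.1) |
| Scheduled EKG | Lost if not yet done |
| Primary completion endpoint | A removed patient has not completed all procedures, so counts against feasibility |

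**The plan's own figure.** Section 9.2 gives 50 patients, 80% power, 70% against 85%, Type I error 0.05. With a one-sided normal approximation:

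n = [(1.645·√(0.70·0.30) + 0.842·√(0.85·0.15)) / 0.15]² = 49.4, rounded up to 50.

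The figure reproduces and is not in dispute. It matters here only because 85% completion implies 0.15 × 50 = 7.5 expected non-completers from all causes.

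**Size of a FLIE shift (illustration).** Section 4.1 says 50 are enrolled; I assume all 50 are dosed. Let k be the number removed before Day 5, p the true impact rate and r the impact rate among those removed. The reported rate is then too low by

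shift = k(r − p) / (50 − k).

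The documents give no removal rate and no FLIE impact rate, so k = 4 or 8 and p = 40% to 80% are assumptions. Results in percentage points (negative means reported too high):

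| Removed patients' impact rate | k | p = 0.4 | p = 0.6 | p = 0.8 |
|---|---|---|---|---|
| All impacted (r = 1) | 4 | 5.2 | 3.5 | 1.7 |
| | 8 | 11.4 | 7.6 | 3.8 |
| Partial linkage, r = (1 + p)/2 | 4 | 2.6 | 1.7 | 0.9 |
| | 8 | 5.7 | 3.8 | 1.9 |
| No linkage (r = p) | 4 or 8 | 0 | 0 | 0 |
| None impacted (r = 0) | 4 | −3.5 | −5.2 | −7.0 |
| | 8 | −7.6 | −11.4 | −15.2 |

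Example: with p = 0.4, 20 of 50 are impacted. Remove 8 of those 20 and 12/42 = 28.6% is reported, 11.4 points below 40%.

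**Comparison with sampling error.** The 95% half-width at n = 50 is 1.96·√(p(1 − p)/50): 13.6 points at p = 0.4 or 0.6, and 11.1 at p = 0.8. Each downward shift in the table is smaller than the half-width at the same p. The interval makes no allowance for selective missingness, so it does not cover the bias by design.

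**The case against.** The case against giving this much weight is reasonable, and much of it stands.

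- **Removals may be few.** Removal is optional, the rescue trigger is the later step of failing secondary interventions, and follow-up lasts six days after dosing. Section 5.4 allows routine breakthrough drugs, urgent intervention and other necessary medication without removal.
- **Safety capture partly fills the gap.** Adverse event records to 30 days should show some worsening nausea or vomiting and its treatment. They do not supply MAT or FLIE scores or the visit table.
- **The numbers are assumed.** The 7.5 expected non-completers cover every cause, including a missed form, so eight early removals for poor CINV would be near a worst case at the planned rate. Removal at the patient's request, for non-compliance or for non-CINV worsening need not track CINV outcome.
- **The affected results are descriptive.** FLIE and MAT have no decision threshold, and 5.3 looks only for trends.
- **Consent wording was not available to this review.** Terms there on data collection after withdrawal could not be checked.

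Three stronger readings are tempting but unsupported. A reader might infer that feasibility is flattered; a removed patient is a non-completer, so it is not. A reader might infer that the EKG is lost selectively in patients at higher QTc risk; nothing links the removal reasons to QTc, and 7.0 adds EKGs for worsening cardiac symptoms during the study period. A reader might infer that failed-rescue patients drop out of the complete-response result; they have already used rescue, so they are known failures if kept in the denominator.

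What remains is that 5.2 itself permits outcome-linked loss of data that could easily be kept.

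**Conclusion.** The point holds in a limited form. Following 5.2 as written can leave the Day 5 FLIE, remaining MAT days, and mainly non-admitted visits outside the centre missing more often in patients with poor CINV control. The EKG point is the loss of a scheduled assessment, nothing more.

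The direction is plausible, not shown, and the size is unknown. If 50 are dosed, 4 to 8 are removed before Day 5 and the true FLIE impact rate is 40% to 80%, the reported rate would be about 1 to 6 points too low under partial linkage, 2 to 11 if every removed patient is impacted, and unchanged or too high otherwise. A reader might build a larger figure by treating every non-completer as an impacted patient removed before Day 5; the documents give no ground for that.

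Only secondary and safety data are affected. The change is still worth making because it is cheap and these data inform the next study.

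**What to change.** **Section 5.2.** State that once the capsule is taken, worsening CINV, use of another antiemetic or non-compliance does not end follow-up. Daily calls, MAT, diary, the Day 5 FLIE and the EKG within its existing Day 3 window continue to Day 7 unless the patient withdraws consent for them.

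**Section 9.3, FLIE.** Report the number of dosed patients without a Day 5 FLIE, and add a sensitivity analysis counting them as impacted. This is a pessimistic bound, not a best estimate. In the worked example it recovers (12 + 8)/50 = 40%. With no linkage it would overstate: (0.4 × 42 + 8)/50 = 49.6%.

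**Section 9.3, complete response.** Keep all dosed patients in the denominator. Count those with emesis or rescue use before removal as non-responders. Report separately those whose status is unknown, with a sensitivity analysis counting them as non-responders.

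**Cost.** A wording change to assessments already scheduled, plus a few extra calls to unwell patients, who may decline. The secondary results may look slightly less favourable.
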